6. *Self-Regulation Mechanisms Hypotheses:* In 4 different fMRI tasks, we hypothesize (a) greater activation of anterior cingulate cortex (ACC) and medial orbitofrontal cortex (OFC) and decreased activation in amygdala/hippocampus after MTPC intervention compared to before intervention (i.e. a pre-post increase) in an emotional Go/NoGo inhibitory control task; (b) greater activation of insula after (compared to before) MTPC in a self-compassion task (that contrasts self-reassurance conditions with a self-criticism condition); (c) greater insula activation during an interoceptive attention task (that contrasts an interoceptive attention condition with an exteroceptive attention condition); and (d) greater rostral ACC (rACC) and ventromedial prefrontal cortex (vmPFC) activation during the anticipation of pain and greater activation in the lateral prefrontal cortex (LPFC) and somatosensory areas during pain in an emotion/pain regulation task, after compared to before the MTPC intervention.
We hypothesize that all inhibitory control and interoceptive targets will be associated with higher levels of initiation of regimen adherence, while self-compassion, interoceptive targets and emotion/pain regulation will be associated with higher levels of regimen maintenance.

HEART Pilot Study Hypotheses

7. ***HEART pilot study validation goal:*** Our goal is to implement activity and heart-rate tracking, nutrition, sleep, and mindfulness practice tracking in a cohort of MINDFUL-PC alumni to determine whether this suite of behavioral monitoring tasks can behaviorally validate the signal from the self-reported action plan initiation protocol.

We hypothesize that self-reported action plan initiation with activity, diet, sleep or mindfulness practice will be associated with a behavioral change as assessed with the daily tracking devices.

8. ***HEART pilot study concurrent cohort:*** We hypothesize that participants who are in an 8-week MTPC group will demonstrate higher levels of action plan initiation, with an associated change in behavioral monitoring, than participants who are randomized to the waitlist condition. We also hypothesize that participants who chose to increase activity will have a greater increase in daily activity than those who chose a diet-, mindfulness- or sleep-related action plan goal.

B. Background and Rationale:

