The **Perceived Control Questionnaire (PCQ)** is adapted from a 5-item perceived control measure from Jerant et al. [55] and a previously validated survey from Armitage et al. [56]. This 5-item scale ask participants to rate their sense of control over chronic illness self-management on a 7-point scale from 1 (*None*) to 7 (*Total*). Items include "How much personal control do you have over your self-management behaviors?" Duration: 3 min.

Action Plan Worksheet/SMART Goal Video: Patient participants will complete the Action Plan Worksheet and watch a brief video about creating SMART goals (for example, <https://www.youtube.com/watch?v=1-SvuFIQjK8>) in PT Study Week 7. The Action Plan Worksheet is a 13-item worksheet that incorporates information about SMART goals to support patient participants to make a goal about their health in one of 3 categories (activity level/exercise, diet/eating/drinking, or mindfulness meditation practice). Patients are encouraged to share this worksheet with a person who may help the patient in accomplishing the goal, and/or a healthcare provider. Duration: 15 min.

Patients will complete the self-report **Action Plan Assessment (APA-10)** questionnaire after filling out the Action Plan Worksheet, at PT Study Week 7. This survey instrument is developed as an adaptation of two self-determination theory scales [57] [58] and incorporates elements of shared decision-making [59] and self-efficacy and barrier appraisal [60]. This 10-item scale evaluates patient behavior in the domains of self-determination, motivation, shared decision-making, and barrier appraisal. Participants are asked to rate their agreement with a statement on

a 7-point scale from 1 (*Strongly Disagree*) to 7 (*Strongly Agree*). A sample item includes “I have agreed to this action plan because I want to do it for myself.” Duration: 5 minutes.

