Patient self-reported **Action Plan Initiation Survey (APIS-5)** will be administered at post-treatment (PT Study Week 8, 12, and 16). This 5-item questionnaire is adapted from a measure used by Guck et al. [56]. In this questionnaire, patients are asked to list their action plan goals generated with their PCP, and determine whether they met or did not meet each goal. Patients are asked to categorize their goals into one of six categories: diet/eating/drinking, exercise/activity, sleep, medication, reducing substance use, and self-care. For each unmet goal, patients are asked to rate the cause of not meeting the goal on an attributional rating scale using a 7-point format. Higher scores indicate internal rather than external and uncontrollable rather than controllable attributions. A sample item includes: “Was the cause of not meeting this goal controllable by you?” where 1 is “Extremely controllable” and 7 is “Not at all controllable.” Duration: 5 minutes. Participants in the HEART pilot study in the concurrent cohort will fill this out as per the main study timeline. Participants in the HEART pilot study alumni cohort will fill this out at the end of HEART study Weeks 4 and 5.

The **Three-Factor Eating Questionnaire-R18 (TFEQ-R18)** is an 18 item questionnaire that refers to current dietary practice and measures 3 different aspects of eating behavior: restrained eating (conscious restriction of food intake in order to control body weight or to promote weight loss), uncontrolled eating (tendency to eat more than usual due to a loss of control over intake accompanied by subjective feelings of hunger), and emotional eating (inability to resist emotional cues). The TFEQ-R18 consists of 18 items on a 4-point response scale (definitely true/mostly true/mostly false/definitely false). Responses to each of the 18 items are given a score between 1 and 4 and item scores are summated into scale scores for cognitive restraint, uncontrolled eating, and emotional eating. An example item includes “Sometimes when I start eating, I just can’t seem to stop.” Duration: 5 minutes.

C.3.f.7. HEART Pilot Study Battery:

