Number of medical visits will be collected through EPIC for each patient for the year before and the six months after randomization. This will include a record of the number of visits with the patient's PCP, the number of outpatient medical visits, the number of inpatient medical stays, and the number of visits to the emergency department (ED). Chronic disease self-management programs have been shown to reduce patient visits to the ED [39]. In order to account for effects of recent health issues and seasonality, ED visits from the past six months and the 7-12 month period prior to study entry will both be used as covariates in the analysis.

Patient no-show rates will also be collected through EPIC as frequency counts from the year before and the six months after randomization. Programs emphasizing patient activation and empowerment have been shown to increase attendance to scheduled patient visits [66]. In order to account for effects of recent health issues and seasonality, attendance rates from the past six months and the 7-12 month period prior to study entry will both be used as covariates in the analysis.

Patient action plans, created by patients and providers at the PCP visit and reported in EPIC, will be reviewed and collected through EPIC. Goal-setting exercises can be used to support chronic illness management [67]. Using these data, a member of the MINDFUL-PC research study team will compile a coded list of patients and their action plan goals.

C.3.f.12. Satisfaction Battery for Patient Participants:

Patient participants will complete the **MTPC Program Satisfaction Survey** after 8 weeks of participation in the study. This 18-item survey contains two parts. First is a series of 12 questions scored on a 5-point Likert scale from 1 (*Strongly Disagree/Poor*) to 5 (*Strongly Agree/Excellent*), with statements such as "I found this program helpful." Next is a series of six open-ended questions in which patients enter a written response to statements including "The most important thing I learned during this program." Duration: 5 min.

C.3.f.13. Adverse Events Reporting Battery for Patients:

The **Adverse Event Patient Participant Self-Report Form** will be completed at the 8-week survey session and 6-month survey sessions. This form asks that parameters be described for each AE. The parameters are detailed below in D.2.

C.3.f.14. Experimental fMRI pilot study screening battery:

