Using an intent-to-treat analysis with 290 patients receiving mindfulness training and 144 patients with orientation only, there will be an 80% chance of detecting a significant difference at a two-sided 0.05 significance level. This assumes that the rate of action plan initiation is 0.54 in orientation only (based on Guck et. al. [70]) and the rate of action plan initiation among patients who receive mindfulness training is 0.68 (based on rates of initiation and maintenance of meditation practice in previous pilot MBIs [94]). After the first twenty participants complete the program, an interim analysis of these pilot data may be used to refine the sample size calculation for RCT.

D. Human Subjects Procedures and Confidentiality

D.1. Confidentiality:

D.1.a. Protection of Subject Privacy:

All of the materials collected are for research purposes only, and data will be kept in strict confidence. No information will be given to anyone without permission from the subject. Confidentiality will be ensured by use of identification codes. All data will be identified with a unique numeric identification code and an acrostic that are unique to the subject. Any data collected before a participant discontinues the study is available for use in this research project.

All research session data will be collected using standardized electronic forms on designed using the REDCap database hosted by Cambridge Health Alliance. REDCap (Research Electronic Data Capture) is a secure, web-based application designed to support data capture for research studies, providing an intuitive interface for validated data entry and export procedures to common statistical packages. All data management will be conducted by the research team operating

from CHA. All data collection will take place under the supervision of the [name] and the Data Manager. Data will only be collected by members of the research team.

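### The plan does not ensure that the goal rated on the APIS-5, which supplies the outcome the trial is sized on, is the goal the patient set on the Action Plan Worksheet

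*Combined protocol and SAP*

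**What the plan says.** **Worksheet.** The Action Plan Study Session in C.3.d.2 and Table 3 of Appendix A have all patients complete a Worksheet in weeks 6-7. C.3.e.4 describes its purpose as helping patients produce their own short-term plan. C.3.f.6 has the patient "make a goal about their health in one of 3 categories (activity level/exercise, diet/eating/drinking, or mindfulness meditation practice". Sharing it with a helper or a healthcare provider is encouraged but not required. Table 3 lists no PCP visit.

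**APIS-5.** The same section, C.3.f.6, says that "patients are asked to list their action plan goals generated with their PCP, and determine whether they met or did not meet each goal", and that the goals are sorted into "one of six categories: diet/eating/drinking, exercise/activity, sleep, medication, reducing substance use, and self-care". C.5.b (hypothesis 5) names the APIS-5 as the measure of initiation and maintenance.

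**Leftover PCP-visit text.** C.3.f.11 states: "Patient action plans, created by patients and providers at the PCP visit and reported in EPIC, will be reviewed and collected through EPIC". A.1 refers to jointly selected plans, C.3.e.4 to a PCP appointment in weeks 6-7, D.4.b.2 to the PCP visit as part of adherence, and D.10.a to a plan made at the PCP visit.

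**Sample size (C.5.c, D.4.c).** The calculation uses "290 patients receiving mindfulness training and 144 patients with orientation only" and assumes that "the rate of action plan initiation is 0.54 in orientation only" and "the rate of action plan initiation among patients who receive mindfulness training is 0.68".

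**HEART.** Hypothesis 7 in A.2.b links initiation of activity, diet, sleep or mindfulness goals to tracked behaviour. Hypothesis 8 expects a larger activity increase in those who chose activity "than those who chose a diet-, mindfulness- or sleep-related action plan goal". C.5.b and D.4.c plan correlations, sleep duration among them, chosen according to the goal in the patient's action plan.

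**The concern.** Two sources for the goal stand side by side in the current text, and nothing says which one is scored. Read literally, the APIS-5 asks about goals from a visit that the schedule does not contain. The natural reading of the survey description is that patients list their goals afresh each time they complete it, although this is not stated outright. No passage ties the answer to the Worksheet, or says how several listed goals become one initiation outcome.

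This matters because the outcome is self-reported in a trial that C.3.c says is not blinded, and only MTPC patients are taught in class how to set health goals (C.3.d.2). If the goal is not fixed in advance, what counts as met can shift towards what was achieved, and the shift could differ by arm. Neither its direction nor its size can be known from the documents, which is why it is better closed by design.

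The category mismatch is a separate problem. It bears on any analysis by type of goal, and so chiefly on HEART.

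**Working it through.** **1. The plan's own power figure.** Inputs from C.5.c: control 0.54 (n = 144), MTPC 0.68 (n = 290), two-sided alpha 0.05.

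- Pooled rate: (144 × 0.54 + 290 × 0.68)/434 = 274.96/434 = 0.6336.
- Null SE: √[0.6336 × 0.3664 × (1/144 + 1/290)] = 0.0491.
- Alternative SE: √[0.54 × 0.46/144 + 0.68 × 0.32/290] = 0.0498.
- Power: Φ[(0.14 − 1.96 × 0.0491)/0.0498] = Φ(0.88) = 81%.

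The stated 80% reproduces. Unpooled, arcsine, continuity-corrected and Fisher versions give 78% to 81%. The arithmetic is sound; the issue is what is being counted.

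**2. The category lists.**

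| Goal | Worksheet | APIS-5 | HEART hypothesis 7 |
|---|---|---|---|
| Activity/exercise | yes | yes | yes |
| Diet | yes | yes | yes |
| Mindfulness practice | yes | not named | yes |
| Sleep | no | yes | yes |
| Medication | no | yes | no |
| Reducing substance use | no | yes | no |
| Self-care | no | yes | no |

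Only two categories appear on both instruments.

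**3. Number of occasions.** C.3.d.2 and Table 3 give five APIS-5 administrations: post-treatment, weeks 9, 10 and 16, and follow-up. C.3.f.6 gives weeks 8, 12 and 16.

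**4. What an unanchored goal could cost in power (illustration).** Assume that a share m of rated goals is unrelated to the Worksheet goal and is met at 0.54 in both arms. The assumption is not in the documents. The MTPC rate becomes 0.54 + (1 − m) × 0.14, and the formula in step 1 gives:

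| m | MTPC rate | Power |
|---|---|---|
| 0 | 0.680 | 81% |
| 10% | 0.666 | 72% |
| 20% | 0.652 | 62% |
| 30% | 0.638 | 50% |

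This covers dilution that is equal in both arms. Drift that differs by arm would bias the estimate itself, and the documents give no basis for a figure.

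**5. HEART.** The smallest correlation detectable with 80% power is tanh[(1.96 + 0.84)/√(N − 3)]. N = 70 gives 0.33 and N = 47 gives 0.40, both as stated in D.4.c. If an analysis is limited to one type of goal, with subgroup sizes assumed here, N = 35 (half) gives 0.46 and N = 17 (about a quarter) gives 0.63. A type that cannot be chosen contributes nothing. C.3.f.7 has both HEART cohorts create their plan on the Worksheet, so under its three-category list there are no sleep goals.

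**The case against.** The APIS-5 itself is not in the documents, and its description may simply be out of date. Its timing disagrees with the schedule. The HEART plan refers to a 7-item initiation survey and to a cut of 5 or more on the APIS-5, neither of which fits five items scored met or not met. The version 1.5 change log, useful only as context, records that the survey was modified to follow the Worksheet. Patients asked for their action plan goals may well name the one they wrote down. This stands, and it rules out several stronger readings:

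- A reader might infer that the rated goal is not the Worksheet goal. The documents show only that nothing guarantees it is.
- A reader might infer that HEART's comparisons by goal cannot run. Hypothesis 8 pools sleep with diet and mindfulness choosers and can run without any sleep goals. The only comparison between goals in C.5.b is exercise against nutrition. The sleep gap also depends on the Worksheet list governing, since the APIS-5 does offer sleep.
- A reader might count patients with mindfulness goals as lost to the powered outcome. A goal is met or not met whatever its category, no split of goals is given, and self-care might absorb such goals.
- A reader might infer that MTPC patients substitute easier goals. No passage says so. Both arms complete the Worksheet and watch the goal-setting video.

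Outdated wording does not remove the point: C.3.f.6 is the only definition of the measure that the analysis section relies on.

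**Conclusion.** The point holds as a conflict within current text over the definition of the outcome in the only main-trial power calculation that states its inputs. The goal source, the category lists and the missing carry-forward rule should be settled before analysis. The defect is in the definition: no stated figure is wrong, and the actual share of mismatched goals is unknown. The power losses in the working rest wholly on the assumed share and on equal dilution in both arms. For HEART the consequence is narrow: if the Worksheet list governs, the sleep element of hypothesis 7 and the goal-dependent sleep-duration correlation have no participants with a sleep goal.

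**What to change.** - For patients who complete a Worksheet, name its goal as the scored goal. Carry its text and category from REDCap into every APIS-5, ask about that goal, and record any new goal separately.
- Use one category list in the Worksheet, the APIS-5 and the HEART analysis, or drop the sleep-goal element.
- Reconcile A.1, C.3.e.4, C.3.f.6, C.3.f.11, C.5.b, D.4.b.2 and D.10.a.
- For data already collected, have staff blind to arm link APIS-5 goals to Worksheets before analysis. Use the matched goals as a sensitivity analysis, and do not discard unmatched records.
- Enrolment was planned from September 2015 (C.4.b), and the change log adds the Worksheet in version 1.5, April 2017. For patients enrolled before it, keep the PCP-visit plan in EPIC as the goal source and report them separately. Counting only matched goals would turn their outcomes into failures or missing values.

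The cost is REDCap set-up, protocol wording and some clerical linking. Initiation rates may come out lower.

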An adverse event (AE) is any untoward medical occurrence in a subject during participation in the clinical study. An adverse finding can include a sign, symptom, abnormal assessment (from vital signs or brain imaging), or any combination of these.

A serious adverse event (SAE) is any AE that results in one or more of the following outcomes:

Death

A life-threatening event

Inpatient hospitalization

A persistent or significant disability/incapacity

A congenital anomaly or birth defect

An important medical event based upon appropriate medical judgment.

D.2.b. Classification of AE Severity:

AEs will be labeled according to severity, which is based on their impact on the patient. An AE will be termed “mild” if it does not have a major impact on the patient, “moderate” if it causes the patient some minor inconvenience, and “severe” if it causes a substantial disruption to the patient’s well-being. Of note, a severe AE and a serious adverse event (SAE) are distinct terms. A subject could experience a severe AE that does not meet the above-listed definition of an SAE; alternatively, a subject could experience a moderate AE that meets the SAE definition.

D.2.c. AE Attribution Scale:

AEs will be categorized according to the likelihood that they are related to the study intervention. Specifically, they will be labeled definitely unrelated, probably related, possibly related, or definitely related to the study intervention.

D.2.c.1. AE Reporting and Follow-up:

This study will comply with the reporting requirements from the Cambridge Health Alliance IRB. The PI will report to the IRB, Independent Monitor, and NCCIH any of the following *unanticipated problems* and *adverse events* that occur 1) during the conduct of the study, 2) after study completion, or 3) after subject withdrawal or completion:

1. *Internal adverse events* that are *unexpected*, and related or *possibly related to the research* and that indicate there are new or increased risks to subjects;
2. *External adverse events* that are *serious*, *unexpected*, and related or *possibly related to the research* and that indicate there are new or increased risks to subjects that require some action (e.g., modification of the protocol, consent process, or informing subjects);
3. *Deviation* from the approved research protocol or plan without IRB approval in order to eliminate apparent immediate hazard to subjects or harm to others;

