4. *Deviation* from the approved research protocol or plan that placed subjects or others at an increased risk of harm regardless of whether there was actual harm to subjects or others;
5. Any event that requires prompt reporting according to the research protocol or investigational plan or the sponsor;
6. Breach of confidentiality or violation of HIPAA (e.g., lost or stolen laptop);
7. Procedural error regardless of whether subjects experienced any harm;
8. Interim analysis, safety monitoring report, publication in a peer-reviewed journal, or other finding that indicates that there are new or increased risks to subjects or others or that subjects are less likely to receive any direct benefits from the research;
9. Complaint by/on behalf of a research subject that indicates that the rights, welfare, or safety of the subject have been adversely affected or that cannot be resolved by the investigator;
10. Incarceration of a research subject during participation in this study (which is not currently approved for involvement of *prisoners* as subjects);
11. *Noncompliance* with applicable regulations or requirements or determinations of the IRB identified by the research team or others that indicates that the rights, welfare, or safety of subjects have been adversely affected;
12. *Suspension* or *termination* of the research, in whole or in part, based on information that indicates that the research places subjects at an increased risk of harm than previously known or recognized;
13. Suspension or disqualification of an investigator by the sponsor, or others;
14. *Scientific misconduct*; or
15. Any other problem that indicates that the research places subjects or others at an increased risk of harm or otherwise adversely affect the rights, welfare or safety of subjects or others.

D.2.c.2. Procedures for collecting and reporting unanticipated problems:

All unanticipated problems (including AEs) will be collected by the PI or other study staff on an AE Tracking Log form, at the following time points: Baseline session, fMRI session (if applicable), on a weekly basis during the intervention (8 weeks), at post study session and at follow-up session, and additionally on an ad-hoc basis.

Reports of *unanticipated problems involving risks to subjects or others* will be submitted to the IRB, IM and NCCIH within 5 working days/7 calendar days of the date the investigator first becomes aware of the problem.

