In some very rare cases, meditation practice can lead to a dissociative state or to psychosis^[95]. This is more likely in participants with current conditions of or a predisposition to psychosis. Patients experiencing active psychosis are excluded from participating in this study. If a participant begins to experience these feelings during his or her time in the study, then the participant may be asked to stop practicing and to meet with either the CMC medical director or the principal investigator for an evaluation. The participant may ultimately be terminated from the study if he or she is experiencing an adverse reaction. These participants may continue to receive other treatments at CHA as part of their ongoing treatment plan.

3. Physical discomfort due to gentle movement aspect of training

The training will involve gentle movements similar in form to hatha yoga. Some participants could experience physical discomfort during this aspect of training. If a participant feels discomfort, he or she will be encouraged to engage in a less straining manner. If discomfort continues, then the participant will be asked to sit out of this brief element of training and discuss the areas of discomfort with their PCP before return to practice of physical postures. Severe discomfort is not expected, but could possibly occur. In this case, the participant will be treated for this pain, and encouraged to return to practice stationary forms of mindfulness.

4. Feelings of embarrassment or anxiety when asked personal survey question.

Some survey questions are of a sensitive or personal nature, and may cause the participant to become upset. In some rare cases, participants may require mental health support upon feeling upset by the survey questions. A patient's referring integrated behavioral health clinician will be contacted if the patient needs additional mental health support. The PI and CMC medical director will remain available to field questions from PCPs about their experience with mindfulness and any adverse experiences. PCPs with adverse events that may influence their fitness to safely practice will be referred to the Employee Assistance Program (EAP) or Physician Health Services. [name], clinical supervisor of the MINDFUL-PC implementation project, will help to monitor and coordinate behavioral health care for participants.

5. Risk of loss of confidentiality

D.2.d.2. Risks to Patients in fMRI study:

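### EPIC inpatient stays are collected for every patient but never compared with the AE log, so unplanned admissions can be absent from the SAE count

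*Combined protocol and SAP*

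**What the plan says.** **Utilisation data.** Section C.3.f.11 states: "Number of medical visits will be collected through EPIC for each patient for the year before and the six months after randomization". The items include "the number of inpatient medical stays, and the number of visits to the emergency department (ED"; D.10.a lists similar items. The section treats them as utilisation. It refers to self-management programmes that reduce ED use, and it makes earlier ED visits covariates.

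**Safety definitions.** Section D.2.a reads: "An adverse event (AE) is any untoward medical occurrence in a subject during participation in the clinical study". It continues: "A serious adverse event (SAE) is any AE that results in one or more of the following outcomes". One listed outcome is "Inpatient hospitalization". Under D.2.c.5, SAEs that are anticipated or unrelated are handled less urgently but still go to the IRB, the Independent Monitor and NCCIH.

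**Safety collection.** Section D.2.c.2 says: "All unanticipated problems (including AEs) will be collected by the PI or other study staff on an AE Tracking Log form". The time points are baseline, any fMRI session, and then "on a weekly basis during the intervention (8 weeks), at post study session and at follow-up session, and additionally on an ad-hoc basis". Section C.3.f.13 adds a patient self-report form at the 8-week and 6-month survey sessions. Section C.3.h adds a question about adverse events for those who discontinue.

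**The concern.** The trial will hold two records that bear on the same events. One covers each patient and does not depend on survey return. The other depends on a patient being in contact and mentioning the event, or on staff hearing of it. Only the second is stated to feed the SAE count.

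The SAE list supports the annual summary of AEs and the judgement on whether AE rates match expectations (D.4.f). It also bears on the first stopping criterion in D.4.d. If an unplanned admission sits in the EPIC extract but not in the log, the safety summary is incomplete by the protocol's own definition, and nothing in the plan would reveal it. If the chance of being logged differs between arms, the comparison of SAEs between arms is distorted as well.

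**Working it through.** The documents state no SAE count, admission rate or AE capture rate, so there is no plan figure to reproduce. The check sets the sections side by side.

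**1. What feeds each record**

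| Source | Section | When | Depends on |
|---|---|---|---|
| AE Tracking Log | D.2.c.2 | set visits, weekly for 8 weeks, ad hoc | staff learning of the event |
| Patient self-report form | C.3.f.13, Table 3 | week 8, month 6 | the form being returned |
| Question at discontinuation | C.3.h | on leaving | the patient being reachable |
| EPIC counts | C.3.f.11, D.10.a | six months after randomisation | the stay being visible in EPIC |

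The first three are AE sources. The fourth is not named as one.

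**2. Where a comparison could have been placed.** The monthly data review (D.2.c.6), the data quality plan and its Table 5 (D.4.a), the safety review plan (D.4.f) and the Independent Monitor reports (D.4.g) do not mention EPIC stays. The analysis plan (C.5.b) has no harms analysis.

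**3. Timing.** After the 8-week intervention, the scheduled AE enquiries are the post-treatment survey (weeks 8-12) and the follow-up survey (weeks 24-26). The sessions at weeks 9, 10 and 16 collect only the APIS-5. The interval without a scheduled AE enquiry is therefore 24 - 12 = 12 weeks to 26 - 8 = 18 weeks. Events in it reach the log through later recall or the ad-hoc route.

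**4. Contact by arm.** MTPC patients attend eight weekly clinician-led sessions and a full day. In weeks 1-8 the scheduled staff call shared by both arms is every two weeks (C.3.d.2). Its five talking points include open prompts but no specific question about AEs or admissions. Section D.2.c.2 calls for weekly collection without saying how this is done in the control arm.

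**5. Why no size can be given.** Let N = 290 + 144 = 434 planned patients, *h* the proportion with a qualifying admission in six months, and *c* the proportion of those captured by the log and forms. Then

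missed = N × h × (1 - c).

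Neither *h* nor *c* is in the documents. With assumed values:

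- h = 0.02, c = 0.90: 434 × 0.02 × 0.10 = 0.9 patients
- h = 0.10, c = 0.50: 434 × 0.10 × 0.50 = 21.7 patients

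The spread, from about 1 to 22, comes wholly from the assumptions.

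**6. Effect of unequal capture.** With equal true risk in both arms, the apparent risk ratio (MTPC to control) is c(MTPC) / c(control). Assumed capture of 0.90 against 0.70 gives 0.90 / 0.70 = 1.29; 0.90 against 0.50 gives 0.90 / 0.50 = 1.80. Equal capture gives 1. These values show the direction and mechanism; they are not estimates.

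**The case against.** The strongest reply is that a utilisation outcome and an AE log can properly coexist, and that the plan has more routes into the log than its fixed visits. The ad-hoc route names no source and does not exclude chart information. Both arms are asked on the calls how they have been, and staff discuss the issues raised twice a week. Patients who discontinue are, if possible, assessed by the investigator. A full DSMP is said to be appended but is not in the text available here. C.1.b.2 also excludes severe mental illness and patients at high risk of hospitalisation, so admissions may be few.

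These routes make capture better than the two self-report forms alone would give, and the low-rate argument is fair. But none of them compares the two records. D.2 says that the DSMP's adverse event reporting guidelines are copied into it, and that text contains no EPIC step; whether the rest of the DSMP contains one is unknown.

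Three stronger readings are tempting, and the documents do not support them.

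- *A reader might infer that every EPIC stay is an SAE.* Under D.2.a the event must be untoward, occur during participation and result in hospitalisation. Planned admissions need not qualify, and stays in the pre-randomisation year do not. C.3.f.11 specifies counts without dates or reasons, so a count alone cannot classify a stay.
- *A reader might infer that the missed events lie mostly among patients who stop responding.* This depends on unknown inputs. If 70% are reached and half of those disclose, 30% are missed through non-contact but 0.70 × 0.50 = 35% among patients who were reached.
- *A reader might infer that EPIC would show the rare harms described in D.2.d.1, where* "meditation practice can lead to a dissociative state or to psychosis"*.* That such harms lead to admission is an inference. The variable is inpatient medical stays; the text does not say whether psychiatric stays count, or whether admissions outside CHA are visible. EPIC is therefore not shown to be a complete or unbiased harm record.

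**Conclusion.** The gap is real but narrow. Followed as written, the plan lets an unplanned post-randomisation admission be recorded in EPIC and be absent from the SAE count, with no step to find the mismatch. Being unrelated is no reason for its absence, given D.2.c.5. Capture may also differ between arms because the intensity of contact does.

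The size of the shortfall cannot be computed from the documents, and no number of missing events should be quoted. The conclusion rests on the available text, without the full DSMP, and applies only to stays that meet D.2.a. It does not affect the efficacy analyses. It should be corrected because the data are already planned and the remedy is cheap.

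**What to change.** In D.2.c.2 and C.5.b, state that:

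- **(a)** EPIC inpatient stays and ED visits in the six months after randomisation are reported by randomised arm for all randomised patients, as patients with at least one and as number of events, and are labelled supportive safety outcomes.
- **(b)** Any patient with more post-randomisation stays in EPIC than in the AE log is flagged. The stay is reviewed in the chart against the existing D.2.a definition and logged if it meets it. It is not entered automatically as an SAE.
- **(c)** The extract's scope is declared: whether psychiatric stays are included, and that admissions outside CHA may be missed.

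Part (a) needs no new data. Part (b) needs limited chart review. C.3.b.1 already provides for EPIC-trained staff, C.3.c keeps the link between study identifier and MRN, and the Closed Safety Report in D.4.g can carry the results by masked group. The cost is protocol wording, that review time, and a higher SAE count in which most added events are likely to be unrelated to the intervention.
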